HMC RESEARCH PROTOCOL

Nurse-led medication self-management intervention in the improvement of medication adherence in adult patients with multi-morbidity: A Feasibility Randomized controlled trial

[name]

[name]

Date-2 Nov 2022

NCT- Not available

1. Summary

Back ground & Aims

Adult patients suffering from multimorbidity are at high risk of medication non-adherence. It has been well established that self-management support is an effective strategy to enhance medication adherence for patients with chronic conditions. However, little is known about the effect of the medication self-management intervention in Adult patients with multimorbidity. The aim of this study to evaluate the effectiveness of a nurse-led medication self-management intervention in improving medication adherence and health outcomes in adult patients with multimorbidity.

Methods

This study is a single centre, single-blind, two-arm randomised controlled trial. Adult patients with multi-morbidity will be recruited from NCCCR Qatar. A total of 100 participants will be randomly allocated to receive standard care or standard care plus the medication self-management intervention. The intervention will be delivered by clinical nurse specialists. The 6-week intervention includes three face-to-face education sessions (2st week, 4rd week and 6th week) and two weekly (8th week and 10 week) follow-up phone calls. Participants in the control group continue to receive all respects of standard care offered by healthcare providers, including chronic disease management, drug prescription, referral to hospital specialists, health education and consultations regarding patients' diseases and treatments during centre visits.

Outcome

The primary outcome is medication adherence as measured by the 5-item Medication Adherence Report Scale. Secondary outcomes include medication self-management capacity (medication knowledge, medication beliefs, and medication self-efficacy), treatment experiences (medication treatment satisfaction and treatment burden). All outcomes will be measured at baseline, immediately post-intervention (7th week), and at 3-month post-intervention.

2. Abbreviations and Acronyms

NCCCR- National Cancer Care Center and Research

CNS- Clinical Nurse Specialist

IMB- Information-Motivation-Behavioral Skills

3. Introduction / Background

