Three clinical nurse specialist as a part of research team from NCCCR will deliver the intervention. Nurses' inclusion criteria are (1) Senior clinical nurses with a Master degree or above, (2) having at least 3 years of working experience in HMC, (3) taking on chronic disease management in routine work, and (4) not planning to quit the job in the next 6 months and Nurses who are participating in other research studies on chronic disease management at the time of this study will be excluded. Nurses will recruit participants through approaching potentially eligible participants in NCCCR. Centre appointments by Clinical nurse specialists will be arranged for interested participants and the principal investigator/ co-investigator will determine the eligibility of participants, describe the study to them, obtain written consent forms, and collect baseline data. A one-week period will be allowed for participants to decide whether or not they wish to participate in the study. Participants' reasons for nonparticipation will be recorded.

Sample size; data collection methods

Sample size

Sample size calculation was performed using G*Power Version 3.1.9.7. Estimation is based upon the primary outcome, medication adherence, at 3 months of follow-up between the intervention and control group. Medication adherence is calculated as sum of the scores from each item using Morisky 8. Based on our recent systematic review and meta-analysis on medication adherence interventions among patients with multimorbidity Cohen's effect size (d) of 0.52 on medication adherence is estimated for a medication self-management intervention program. The required sample size will be 94 participants (47 in the intervention group and 47 in the control group) to attain an 80% power with a two-sided α of 0.05. Therefore, for a 5% attrition rate, the final sample size required is 100 participants.

For Arabic speaking patients, the questions will be translated to Arabic by the Arabic speaking research team member.

Randomization & blinding

Consenting participants will be randomized in outpatient clinic in NCCCR. Randomization will be block randomization, and generated by a computer program centrally (Nursing/ Midwifery Research department).

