Our primary analysis will be the ‘intention-- to-treat’ population, which will include all randomized patients analyzed according to their original treatment allocation, irrespective of their subsequent adherence or how they were actually treated. All data will be analyzed using STATA 17.0 software. Descriptive statistics will be used to describe and compare socio-demographic data on participants between the intervention and control group. Continuous variables that follow a normal distribution will be expressed as means and standard deviations, whereas categorical variables will be presented as frequency counts and percentages. Median values and interquartile ranges will be calculated for continuous data with a skewed distribution. Mann-Whitney U-test or t-test will be performed for continuous data to compare baseline characteristics between groups, and Chi-squared test or Fisher’s exact test will be used for categorical variables. The distributions of the outcome variables will be evaluated, and normalizing transformation will be applied as needed. Primary and secondary outcomes will be analyzed following the intention to treat principle at the individual participant level. Changes in repeated outcome measures across different time points between the intervention and control group will be analyzed using generalized estimating equation models with adjustment for potential confounders of the baseline variables. All statistical tests are two-sided, and $p < 0.05$ will be statistically significant.

9. Adverse Event Reporting

In this section, provide a definition of anticipated adverse events that are related to the research, including a description of how SAEs will be assessed, tracked and reported

There will not be any adverse events related to intervention because it is educational intervention. If some adverse event related to outcome reported during the study, we will notify to the IRB.

10. Ethical Consideration

A statement that the study will be conducted in full conformance with principles of the “Declaration of Helsinki”, Good Clinical Practice (GCP) and within the laws and regulations of MoPH in Qatar.

The study will be conducted in full conformance with principles of the “Declaration of Helsinki”, Good Clinical Practice (GCP) and within the laws and regulations of MoPH in Qatar.

11. Sponsor, Funding & Collaborator Information

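### Section 8 names no deciding visit or model term for the primary outcome, so the GEE analysis as written is not the single 3-month comparison that was sized

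*Combined protocol and SAP*

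**What the plan says.** **Sizing (section 6, Sample size).** "Estimation is based upon the primary outcome, medication adherence, at 3 months of follow-up between the intervention and control group". The standardised effect is d = 0.52, and the target is to "attain an 80% power with a two-sided α of 0.05". The result is "94 participants (47 in the intervention group and 47 in the control group"), raised to 100 for 5% attrition.

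**Visits (section 1, Outcome).** "All outcomes will be measured at baseline, immediately post-intervention (7th week), and at 3-month post-intervention". Section 5 and the outcome assessment part of section 7 repeat this schedule and call the visits T0, T1 and T2. The randomisation text in section 6 instead places the last data collection at week 12.

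**Analysis (section 8).** "Changes in repeated outcome measures across different time points between the intervention and control group will be analyzed using generalized estimating equation models", adjusted for baseline confounders that are not listed. All tests are two-sided with a 0.05 threshold.

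Section 8 names no primary visit, contrast or order of testing. The primary objective (section 4) and the primary outcome text (section 7) name no time point either.

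**The concern.** A three-visit GEE can yield several between-arm tests of Morisky-8: the T1 contrast, the T2 contrast, a joint two-degree-of-freedom arm-by-visit test, or an effect averaged over T1 and T2. All of them fit section 8, they can disagree, and nothing in that section prevents the choice from being made once results are known.

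Two things are at stake. If significance at T1 or at T2 were each accepted as success, the primary outcome would have two chances at 0.05. If the joint test were used, it would answer a different question from the one sized. It asks whether the arms differ at any follow-up visit, and it can be positive when there is no effect at 3 months.

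**Working it through.** **Inputs from the plan.** Two-sided alpha 0.05; d = 0.52; 47 per arm before attrition; follow-up visits T1 and T2.

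**Assumptions, not in the plan.** The correlation ρ between the T1 and T2 between-arm contrasts (0 to 0.9), and the effect at T1. Outcome variance is set to 1 at each visit. Eligibility confines the baseline Morisky score to zero or, in another sentence, to below 2, so change and level contrasts should differ little.

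**Step 1. The plan's own figure.** A two-sided two-sample t-test at d = 0.52 and 80% power needs 60 per arm (59 by normal approximation), 120 in total. The stated 94 is not reproduced. A one-sided 0.05 t-test needs 47 per arm, which gives 94. For attrition, 94 / 0.95 = 98.9, so 99; the stated 100 is consistent.

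**Step 2. Power of the comparison that was sized.** The noncentrality is 0.52 × √(47/2) = 2.52. Normal approximation: P(Z > 1.96 − 2.52) = 71%. The noncentral t gives 70% with 47 per arm and 73% if all 50 per arm are analysed. The shortfall from 80% is there before any question about the GEE arises.

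**Step 3. Type I error by decision rule.**
- One T2 contrast, or one joint test: 5%.
- Success at either T1 or T2, each at 0.05: 1 − P(|Z1| < 1.96 and |Z2| < 1.96), with Z1 and Z2 bivariate normal with correlation ρ.

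| ρ | Error rate, either visit |
|---|---|
| 0 | 1 − 0.95² = 9.75% |
| 0.3 | 9.5% |
| 0.5 | 9.1% |
| 0.7 | 8.3% |
| 0.9 | 7.0% |

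**Step 4. The joint test.** With effects d1 at T1 and d2 at T2, the noncentrality is λ = (47/2) × (d1² − 2ρ·d1·d2 + d2²) / (1 − ρ²). Power is the probability that a noncentral chi-square on 2 df exceeds 5.99. Note that (47/2) × 0.52² = 6.354.

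- *Effect at T1 only* (d1 = 0.52, d2 = 0): λ = 6.354 / (1 − ρ²).
- *Same effect at both visits* (0.52): λ = 12.709 / (1 + ρ).
- *Smaller effect at T1* (d1 = 0.26, d2 = 0.52): general formula.

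| ρ | T1 only | Same at both | 0.26 then 0.52 | T2 contrast (d2 = 0.52) |
|---|---|---|---|---|
| 0.3 | 65% | 81% | 63% | 71% |
| 0.5 | 74% | 74% | 61% | 71% |
| 0.7 | 90% | 69% | 65% | 71% |

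The T1-only column is the chance of a significant joint test with no effect at the visit that was sized. The next two columns show that, when there is an effect at T2, the joint test can have more or less power than the T2 contrast.

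**The case against.** The best reply is that the sample size paragraph already identifies T2. It ties the calculation to "medication adherence, at 3 months of follow-up between the intervention and control group", and a GEE with an arm-by-visit term can supply exactly that contrast, so choosing GEE does not contradict the sizing. This stands in part: T2 is the natural reading of the intention. But a sizing assumption is not a decision rule, section 8 does not refer back to it, and the timing of T2 is itself given in two ways.

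A reader might also infer that the plan's error rate is wrong, at 8% to 10%. The documents do not support that. No sentence says that a result at either visit counts as success; the 0.05 threshold is a general one, and a single contrast or a single joint test keeps 5%. The rate is undetermined.

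Nor do the documents show that the GEE lowers power. The losses to 61% to 65% need an assumed T1 effect of 0.26, half that at T2. With 0.52 at both visits the joint test has 81% to 69% over correlations 0.3 to 0.7.

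The title calls this a feasibility trial, which softens the matter somewhat. The primary objective, however, is to evaluate effectiveness, and the trial is sized for a hypothesis test.

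**Conclusion.** The point holds as a mismatch between two stated rules: one 3-month comparison sets the sample size, while an analysis across all visits with no named deciding test is to be run. The omission is plain from the text and rests on no assumption.

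Its size does rest on assumptions. Type I error on the primary outcome lies between 5% and about 10%, depending on the rule adopted and on a T1–T2 correlation that the plan does not give. A joint test would be significant 65% to 90% of the time (correlations 0.3 to 0.7) with d = 0.52 at T1 and nothing at T2. The direction of any power difference cannot be settled without a T1 effect.

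The gap between 80% and about 70% is a separate sample size error. It should not be blamed on the GEE, and naming T2 will not close it. The point must be fixed before outcome data are seen, because until then the primary result is not uniquely defined.

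**What to change.** Add to section 8, before anyone sees outcome data: the primary test is the between-arm difference in mean Morisky-8 at T2, estimated from the arm-by-visit term of the GEE, at two-sided alpha 0.05; the T1 contrast and the joint arm-by-visit test are secondary.

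In the same amendment:
- Reconcile the timing of T2, which is 3 months after the intervention in sections 1, 5 and 7 but week 12 in the randomisation text of section 6.
- List the baseline covariates, so that the primary model is fully specified.
- Restate the power separately. At d = 0.52, two-sided, 47 per arm gives about 70%. Reaching 80% needs 60 per arm: 120 / 0.95 = 126.3, so 127 after 5% attrition, or 128 for equal arms.

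The wording costs one sentence and a short covariate list. The downside is that an effect seen only at T1 can no longer be claimed as the primary result. Correcting the power costs either more participants or an openly lower stated power.

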The participants of the trial are discharged adult patients with multi-morbidity. Multi-morbidity is defined using a cut-off of three or more chronic conditions as patients with at least three conditions are more likely to have complex needs and great utilization of healthcare services (28). To avoid the ceiling effect and improve study power to detect changes in adherence, only participants with low medication adherence (Morisky scale < 2) are considered eligible for the trial.

Participants' **inclusion criteria** are

- +18 years old or over,
- patients with **at least two of the** identified comorbidities (Hypertension, Chronic painful condition, Cancer, Inflammatory connective tissue disorders, Diabetes, Lipid disorder, Dyspepsia and gastroenteritis, Heart disease, Chronic obstructive pulmonary disease, Stroke and cerebrovascular disease , chronic kidney disorder , Asthma Thyroid disorders, Anemia, Chronic liver disease, Depression, Epilepsy, Anxiety & other stress related disorders), (3) having at least one medication prescribed for a chronic condition over at least the 3 months prior to inclusion in the study,
- non-adherence to medications, as defined by scoring zero on the 8-item Medication Adherence Report Scale (Morisky -8)(29),
- independently managing their medications (i.e., not rely on a care taker),
- able to speak or understand English/Arabic,
- able and willing to receive phone calls, and
- capable of providing a written informed consent to participate in the study.

Exclusion criteria are

- being institutionalized in a long-term care facility,
- planning to move away from the community in the next 6 months,
- cognitive impairment (Mini-cog scores < 4), and
- currently participating in research involving chronic disease management. Patients with cognitive impairment are excluded because they may not be able to provide valid answers to the questionnaires.

[figure not shown]

Fig2. Theoretical framework of the study: the extended information motivation behavioral skills model of medication adherence

Recruitment

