Based on screening & randomization tool

Risk

In this section describe the anticipated risks associated with participation in the research (i.e. illness, injury, death)

No risk is anticipated as part of study

Bio-Specimens & Sample Collection

In this section describe what specimens or samples will be collected specifically for research, if specimens will be stored long-term and/or destroyed. Consider what happens to data/specimens if subject withdraws consent

NA

Outcomes

In this section provide details on the outcome measures and the anticipated primary & secondary outcomes

Outcome assessment

The nurses masked to the participant allocation will collect follow-up data through telephone interview. Participants will be assessed at baseline (T0), in the week immediately post-intervention (7th week) (T1), and at 3-month post-intervention (T2). Table 2 provides an overview of primary and secondary outcomes as well as covariates at each time point. Permission will be obtained from the original authors to use the scales for this study.

Primary outcome

Medication Adherence

The English version of Morisky-8 will be administered to assess medication adherence of the participants(29). The Morisky-8 is a self-reporting measure of unintentional and intentional medication non-adherent behaviors with a yes and no response. The total score of the moresky-8 ranges from 0 to 8, with a higher score representing higher adherence to medication.

Table 2 Schedule of enrolment, interventions, and assessments

TIMEPOINT	STUDY PERIOD				
	Enrolment	Baseline T0	Intervention	Follow-up	
				T1	T2
ENROLMENT					
Eligibility screen	X				
Informed consent	X				
Allocation		X			
INTERVENTION					
Intervention group			X		
Control group			X		
ASSESSMENTS					
Primary outcome					
Medication adherence (Moresky-8)		X		X	X
Secondary outcomes					
Medication knowledge (PKMUQ)		X		X	X
Medication beliefs (BMQ)		X		X	X
Medication self-efficacy (SEAMS)		X		X	X
Treatment burden (TBQ)		X		X	X
Potential covariates					

Socio-demographics questionnaire)	(Patients	X
Number of prescribed medications (one-item question)		X
Depressive symptoms (PHQ-9)		X

Secondary

outcomes

Medication Knowledge

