The treatment burden will be measured by the 10-item Multi-morbidity Treatment Burden Questionnaire (MTBQ)(36). It assesses the wide range of behavioral and emotional burdens involved in treatment implementation and treatments associated with taking multiple medicines, self-monitoring their health and making lifestyle changes. Each item is scored on 6-point Likert scale, ranging from 0 = does not apply to 5 = most difficult. Scores are summed to derive a total score ranging from 0 to 50 with a higher score indicating a higher level of treatment burden.

Potential covariates

Socio-demographic characteristics and the number of prescribed medications

Socio-demographic characteristics will be collected at baseline from patients. Patients will be asked about age, gender, educational level, marital status, monthly income, and the number of prescribed medications.

Intervention fidelity and contamination

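### The planned GEE does not say how each outcome's baseline score is used, and its natural reading loses precision on the secondary scales

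*Combined protocol and SAP*

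**What the plan says.** Section 8 gives one sentence on the model: "Changes in repeated outcome measures across different time points between the intervention and control group will be analyzed using generalized estimating equation models", and the adjustment is for "generalized estimating equation models with adjustment for potential confounders of the baseline variables". It does not list the responses, say whether the arms share a baseline mean, or name a working correlation, a type of standard error or the covariates.

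The candidate covariates are in section 7. Table 2 lists socio-demographics, number of prescribed medicines and PHQ-9 as potential covariates. The text under Potential covariates says "Patients will be asked about age, gender, educational level, marital status, monthly income, and the number of prescribed medications". Neither place names an outcome's own baseline score.

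Those scores will exist. Under Outcome assessment, "Participants will be assessed at baseline (T0), in the week immediately post-intervention (7th week) (T1), and at 3-month post-intervention (T2"), and Table 2 marks Morisky-8, PKMUQ, BMQ, SEAMS and treatment burden at all three times.

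Two further passages bear on the point:

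- Section 8 also plans baseline tests: "Mann-Whitney U-test or t-test will be performed for continuous data to compare baseline characteristics between groups".
- Section 6 restricts entry on the primary scale in two different ways. One sentence requires a Morisky score below 2. The inclusion list requires "non-adherence to medications, as defined by scoring zero on the 8-item Medication Adherence Report Scale" (labelled there as Morisky-8).

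**The concern.** A model for change over T0, T1 and T2 usually has T0 among the responses and takes the time-by-arm interaction as the treatment effect. If each arm has its own baseline mean, that interaction is a difference in change scores. It carries the full noise of the baseline measurement. Adjusting for the baseline score never has larger variance in large samples, and usually has smaller. It also removes chance imbalance on the variable that normally predicts follow-up best.

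The stake is the secondary objective. PKMUQ, BMQ, SEAMS and treatment burden have no entry restriction, so their baselines should carry information. The trial is small, and this information is already being collected.

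Morisky-8 raises a different issue. Its T0 value is constant or nearly so by design. It does not belong in a response vector that assumes one variance and one correlation across visits.

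**Working it through.** **Inputs.** From section 6 (Sample size): 47 per arm evaluable, standardised effect 0.52, two-sided 0.05, 80% power. The 0.52 is stated for adherence only and is used for the other scales purely as an illustration. The documents give no baseline-to-follow-up correlation r, so 0.3, 0.5 and 0.7 are assumed. Follow-up SD is set to 1.

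**Step 1: the plan's own figure.** A two-sided two-sample t-test with effect 0.52 needs 60 per arm (120 in all) for 80% power, not 47 (94). At 47 per arm, power is 70.3%. The figure of 94 reproduces only with a one-sided 0.05 test (80.4%). That is a separate problem. Here it sets the unadjusted benchmark at 70.3%.

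**Step 2: unrestricted scales.** With equal SDs at T0 and follow-up, variance relative to a follow-up-only comparison is:

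- change contrast with arm-specific baseline means: 2(1 − r)
- baseline-adjusted (ANCOVA): 1 − r²
- ratio: 2(1 − r)/(1 − r²) = 2/(1 + r)

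Power uses the noncentral t with noncentrality (0.52/√V) × √(47/2), where √(47/2) = 4.848. At r = 0.5 the adjusted value is (0.52/√0.75) × 4.848 = 2.91, giving 82.1%. The change value is 0.52 × 4.848 = 2.52, giving 70.3%.

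| r | V change | V adjusted | Ratio | Power, change | Power, adjusted | N for 80%, change vs adjusted |
|---|---|---|---|---|---|---|
| 0.3 | 1.40 | 0.91 | 1.54 | 55.9% | 74.4% | 166 vs 108 |
| 0.5 | 1.00 | 0.75 | 1.33 | 70.3% | 82.1% | 120 vs 90 |
| 0.7 | 0.60 | 0.51 | 1.18 | 89.6% | 93.7% | 72 vs 62 |

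**Step 3: is T0 as a response the cause?** A simulation with 47 per arm, exchangeable correlation and 400 runs per r gave these empirical standard errors for the T2 effect:

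| r | GEE, baseline means free by arm | GEE, common baseline mean | ANCOVA |
|---|---|---|---|
| 0.3 | 0.237 | 0.198 | 0.200 |
| 0.5 | 0.194 | 0.166 | 0.166 |
| 0.7 | 0.154 | 0.140 | 0.139 |

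Monte Carlo error on each is about 1/√(2 × 400) = 3.5%. Keeping T0 as a response costs nothing when the arms share one baseline mean. The loss comes from the free means.

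**Step 4: Morisky-8.** If everyone enters at 0, change equals the follow-up score and power is 70.3% either way. As a covariate, T0 would be collinear with the intercept. If entry is below 2, T0 takes the values 0 and 1, with SD at most 0.5. With an assumed follow-up SD of 2, the SD ratio is k = 0.5/2 = 0.25, and the change variance is 1 + k² − 2rk:

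| r within trial | V change | V adjusted | Power, change | Power, adjusted |
|---|---|---|---|---|
| 0 | 1.06 | 1.00 | 67.7% | 70.3% |
| 0.1 | 1.01 | 0.99 | 69.8% | 70.8% |
| 0.3 | 0.91 | 0.91 | 74.3% | 74.4% |

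The gain is about 0 to 3 points. It depends on k: a follow-up SD of only 1 (k = 0.5) would give 60.7% against 70.3% at r = 0.

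**The case against.** The strongest reply is that this is a gap in specification and not a demonstrated error. Most of that stands, and it rules out several stronger readings.

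- A reader might infer that T0 is definitely a response and that the baseline score is definitely left out. Section 8 states neither. Its reference to baseline variables could be meant to include the baseline outcome, and Table 2 calls its covariates potential.
- A reader might infer that having T0 as a response is itself what loses precision. Step 3 shows that it is not.
- A reader might infer that baseline adjustment would make up the power shortfall on the primary outcome. The entry restriction on Morisky-8 leaves almost nothing to adjust for.
- A reader might infer that the planned baseline tests will select the covariates. The plan describes them only as a comparison of the groups. Because section 8 leaves its confounders unnamed, the possibility is open, but it is not stated.
- The power figures borrow an adherence effect size. The documents give no effect size or power claim for the secondary scales. The variance ratios do not depend on it.
- GEE mean estimates remain consistent under a wrong working correlation, and robust standard errors protect inference. That answers the worry about a near-constant T0, provided robust errors are used, and the plan does not say so.
- Modelling only T1 and T2 drops randomised participants with no follow-up score, although sections 7 and 8 promise to include all who are randomised. This is a real trade-off, and it is why the fix offers a second model.

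What remains is that no outcome's own baseline score is named anywhere as a covariate, and that the natural reading is the less efficient model.

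**Conclusion.** The point holds as an under-specification with a likely, avoidable cost on the secondary outcomes. If baseline means are free by arm, the variance of those treatment effects is inflated by 18% to 54% over the assumed range r = 0.7 to 0.3. In the illustration this is worth about 4 to 18 power points (93.7 − 89.6 and 74.4 − 55.9). The variance ratios rest on equal variances at T0 and follow-up and on the assumed r. The power figures also rest on the borrowed effect of 0.52.

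For the primary outcome the cost is nil under the zero-score criterion and about 0 to 3 points under the below-2 criterion with k near 0.25. The documents do not support a claim that the primary analysis loses material power through baseline handling. The conflict between the two entry thresholds does matter, because it decides whether the Morisky-8 baseline varies at all.

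**What to change.** Amend section 8 to state the following.

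- **Secondary outcomes (PKMUQ, BMQ subscales, SEAMS, treatment burden).** Choose one of two models in advance:
  - T1 and T2 as responses, with arm, visit, arm-by-visit and the same scale's T0 score as covariate; or
  - T0, T1 and T2 as responses, with a baseline mean common to both arms. This matches ANCOVA precision and keeps randomised participants who have no follow-up score. It needs a named working correlation other than independence, because under independence the estimate reverts to a follow-up-only comparison.
- **Morisky-8.** Model T1 and T2 only, and include T0 as a covariate only if it varies. Reconcile the two entry thresholds in section 6 so that this is known beforehand.
- **Standard errors.** Robust (sandwich) for all outcomes.
- **Covariates.** Name the set in advance from Table 2 and the Potential covariates text, which differ on PHQ-9, and adjust for it whatever the observed balance. State that baseline significance tests will not be used to choose covariates.

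The cost is analysis wording only: no new data, visits or participants. The one choice to weigh is between the two secondary-outcome models, given the commitment to analyse everyone randomised.
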